8.7.2. Descriptive Analysis by Objective

1. Both clinical and demographic characteristics will be described for each newly AML and R/R B-cell ALL patients cohorts and for overall cohort (both novo AML and R/R B-cell ALL). No statistical testing will be carried out for demographic or clinical characteristics. Only descriptive data will be reported (absolute number, frequency, mean \pm standard deviation, median, interquartile range, minimum or maximum).

Demographic characteristics at diagnosis

- Age at diagnosis
- Gender (Female, Male)
- Race/Ethnicity

- County of residence
- Health insurance type.

Clinical data description for newly AML patients at diagnosis

- Comorbidities at newly AML diagnosis;
 - Anxiety
 - Cardiovascular disease
 - Cerebrovascular disease
 - Chronic pulmonary disease
 - Depression
 - Diabetes
 - Dyslipidemia
 - Hypertension
 - Hepatitis B
 - Hepatitis C
 - HIV/AIDS
 - Human cytomegalovirus (HCMV)/herpes
 - Gastrointestinal disease
 - Liver disease
 - Obesity
 - Renal disease
 - Thyroid disease
 - Other
- Family history of hematological malignances;
- Prior exposure to toxic agents;
- Prior exposure to a high dose of radiation;
- Reason for the exposure: therapeutic radiation for other cancers; accidental exposures, or other (description);
- Bleeding history;
- Tobacco consumption habits.
- Eastern Cooperative Oncologic Group (ECOG) performance status result
- Karnofsky performance status (KPS)
- Year of diagnosis

Clinical data description for R/R B-cell ALL patients at diagnosis

- Comorbidities at newly R/R B-cell ALL diagnosis
- Family history of hematological malignances;
- Prior exposure to toxic agents;
- Prior exposure to a high dose of radiation;
- Reason for the exposure: therapeutic radiation for other cancers; accidental exposures, or other (description);
- Bleeding history;
- Tobacco consumption habits.
- ECOG performance status result
- KPS
- Year of diagnosis

2. For each treatment line, treatment pattern will be described for each newly AML and R/R B-cell ALL patients cohorts. No statistical testing will be carried out. Only descriptive data will be reported (absolute number, frequency, mean \pm standard deviation, median, interquartile range, minimum or maximum) for:

Newly AML patients:

Effective Date: 01Feb2022

- Classification of patient for the standard AML therapy;
- Drug regimen prescribed;
- Gemtuzumab, midostaurin or venetoclax associated with the treatment;
- Regimen type;
- Treatment duration;
- Time to next treatment;
- Total number of cycles;
- Patients that withdraw and reasons for withdrawing
- Dose reduction
- CNS involvement at disease progression
- Radiotherapy
 - Duration, dose, and local of application
- Intrathecal chemotherapy
 - Drug administered intrathecally
- Stem cell transplant (SCT)
 - Laboratory exams for SCT
 - Post-transplant event
- Laboratory exams before and after treatment line

R/R B-cell ALL patients:

- Regimen type
- Drug regimen prescribed
- Treatment duration
- Time to next treatment
- Total number of cycles
- Patients that withdraw and reasons for withdrawing
- CNS involvement at disease progression
- Radiotherapy
 - Duration, dose, and local of application
- Intrathecal chemotherapy
 - Drug administered intrathecally
- Stem cell transplant (SCT)
 - Laboratory exams for SCT
 - Post-transplant event
- Laboratory exams before and after treatment line

Secondary Objective(s)

3. For each treatment line, only descriptive data (absolute number, frequency, mean ± standard deviation, median, interquartile range, minimum or maximum) will be described for cytogenetic and/or molecular testing and immunophenotyping for each newly AML and R/R B-cell ALL patients cohorts:

newly AML and R/R AML

- Molecular test performed
- AML translocation result
- Molecular profile;
- AML WHO classification
 - AML with recurrent genetic abnormalities
 - AML with t(8;21)(q22;q22.1);RUNX1-RUNX1T1
 - AML with inv(16)(p13.1q22) or t(16;16)(p13.1;q22);CBFB-MYH11

- APL with PML-RARA
- AML with t(9;11)(p21.3;q23.3);MLLT3-KMT2A
- AML with t(6;9)(p23;q34.1);DEK-NUP214
- AML with inv(3)(q21.3q26.2) or t(3;3)(q21.3;q26.2); GATA2, MECOM
- AML (megakaryoblastic) with t(1;22)(p13.3;q13.3);RBM15-MKL1
- Provisional entity: AML with BCR-ABL1
- AML with mutated NPM1
- AML with biallelic mutations of CEBPA
- Provisional entity: AML with mutated RUNX1
- AML with myelodysplasia-related changes
- Therapy-related myeloid neoplasms
- AML, NOS
- Immunophenotyping result

newly B-cell ALL and R/R B-cell ALL

- Molecular test performed
- Molecular profile;
- ALL cytogenetic risk classification according to WHO for B-lymphoblastic leukemia/lymphoma
 - B-lymphoblastic leukemia/lymphoma, NOS
 - B-lymphoblastic leukemia/lymphoma with recurrent genetic abnormalities
 - B-lymphoblastic leukemia/lymphoma with t(9;22)(q34.1;q11.2);BCR-ABL1
 - B-lymphoblastic leukemia/lymphoma with t(v;11q23.3);KMT2A rearranged
 - B-lymphoblastic leukemia/lymphoma with t(12;21)(p13.2;q22.1); ETV6-RUNX1
 - B-lymphoblastic leukemia/lymphoma with hyperdiploidy
 - B-lymphoblastic leukemia/lymphoma with hypodiploidy
 - B-lymphoblastic leukemia/lymphoma with t(5;14)(q31.1;q32.3) IL3-IGH
 - B-lymphoblastic leukemia/lymphoma with t(1;19)(q23;p13.3);TCF3-PBX1
 - Provisional entity: B-lymphoblastic leukemia/lymphoma, BCR-ABL1-like
 - Provisional entity: B-lymphoblastic leukemia/lymphoma with iAMP21
- Immunophenotyping result

4. For each cytogenetic and/or molecular testing for newly AML, the risk stratification will be described with frequencies and absolute percentages for each treatment line:

newly AML and R/R AML

- AML cytogenetic risk classification according to 2017 European LeukemiaNet (ELN)
 - Favorable
 - Intermediate
 - Poor/Adverse

R/R B-cell ALL

- ALL cytogenetic risk classification
 - Good prognosis
 - Intermediate prognosis
 - Poor prognosis
 - Undetermined prognosis

5. Data from previous treatment lines from diagnose until study inclusion will be described for newly B-cell ALL patients and R/R B-cell ALL patients. For each treatment line, no statistical testing will be carried out. Only descriptive data will be reported (absolute number, frequency, mean ± standard deviation, median, interquartile range, minimum or maximum) for:

Newly B-cell ALL patients (treatment lines from ALL diagnose until study inclusion)

- ALL cytogenetic risk classification
- Regimen type.
- Drug regimen prescribed
- Treatment duration
- Time to next treatment
- Total number of cycles
- Number of patients with dose reduction;
- Number of patients with regimen withdraw;
 - Reasons of regimen withdraw;
- Radiotherapy
 - Duration, dose, and local of application
- Intrathecal chemotherapy
 - Drug administered intrathecally
- Stem cell transplant (SCT)

6. Clinically relevant events of newly AML and R/R B-cell ALL patients will be describe by treatment line and data will be reported as absolute number, frequency, mean ± standard deviation, median, interquartile range, minimum or maximum for:

newly AML

- Period of start of the event from start of first-line treatment;
- Clinical event description;
 - Hematological toxicities;
 - Gastrointestinal toxicities;
 - Hepatotoxicity.
- Most common adverse events description

R/R B-cell ALL

- Period of start of the event from start of first-line treatment;
- Clinical event description;
 - Hematological toxicities;
 - Gastrointestinal toxicities;
 - Hepatotoxicity.
- Most common adverse events description

7. To each newly AML and R/R B-cell ALL patients, the EFS will measure time since the date of initiation of treatment (or newly AML diagnosis and newly ALL diagnosis, if the previous is not available) until i) treatment end date (or treatment start date of the next treatment line, if the previous is not available) when treatment response was Refractory disease(5) or Relapsed from CR or CRI or recurrent disease(6); i) date of death, whichever comes first. This time-to-event analysis will be described summarized in tables and using Kaplan Meier methods and plot, if appropriate. Patients not known to have any of these events are censored on the date they were last examined:

newly AML

- Descriptive (median and CI(95%) estimations of Kaplan-Meier) of EFS;
- Time categorized count and percentages.

R/R B-cell ALL

- Descriptive (median and CI(95%) estimations of Kaplan-Meier) of time between treatment initiation and R/R event in months;

- Time categorized count and percentages.

8. The OS will be measure for both newly AML and R/R B-cell ALL patients as median time since newly diagnosis or treatment initiation until death from any cause. This time-to-event analysis will be described using a Kaplan Meier plot, if appropriate

newly AML

- Descriptive (median and CI(95%)) estimations of Kaplan-Meier) of time between date of diagnosis or treatment initiation and R/R event in months;
- Time categorized count and percentages.

This analysis will also be described for fit and non-fit newly AML patients.

R/R B-cell ALL

- Descriptive (median and CI(95%)) estimations of Kaplan-Meier) of OS;
- Time categorized count and percentages.

9. The median OS and the percentage (and 95% confidence intervals) of alive patients in 1, 3- and 5-years, if feasible, follow up of newly diagnosed or treatment initiation AML and R/R B-cell ALL patients will be assessed. The OS will be defined as median time since newly diagnosis or treatment initiation until death from any cause. This time-to-event analysis will be described using a Kaplan Meier plot, if appropriate.

newly AML

- Descriptive (median and CI(95%)) estimations of Kaplan-Meier) of time between treatment initiation and death in months;
- Time categorized count and percentages.

This analysis will also be described for fit and non-fit newly AML patients

R/R B-cell ALL

- Descriptive (median and CI(95%)) estimations of Kaplan-Meier) of time between treatment initiation and death in months;
- Time categorized count and percentages.

10. For all AML patients who achieved Complete remission/response (CR) or Complete remission/response with incomplete hematological/count recovery (CRI) at the end of treatment, the RFS analysis will consider the treatment end date until date of next treatment initiation or date of death, whichever comes first. This time-to-event analysis will be described using a Kaplan Meier plot, if appropriate.

newly AML

- Descriptive (median and CI(95%)) estimations of Kaplan-Meier) of RFS
- Time categorized count and percentages.

11. For newly AML patients, each treatment response (induction and consolidation therapy) will assess the proportion of patients who achieve complete remission (CR), complete remission with incomplete haematological recovery (CRI), complete remission without minimal residual disease (MDR-), partial remission (PR), and progressive disease. No statistical testing will be carried out. Only descriptive data will be reported (absolute number, frequency, mean \pm standard deviation, median, interquartile range, minimum or maximum) for.

Newly AML patients:

- Treatment response
 - CR,
 - CRI,
 - partial remission/response,
 - progressive disease,
 - refractory disease,
 - relapsed from CR or CRI or recurrent disease,
 - other
- Minimal residual disease (MRD) evaluation for patients that achieved CR or CRI and the diagnose method for MRD evaluation
- Patient status description

12. For R/R B-cell ALL patients, each treatment response (to rescue treatment) will access the proportion of patients with complete remission (CR), complete remission without minimal residual disease (MRD-), partial remission (PR), and progressive disease. No statistical testing will be carried out. Only descriptive data will be reported (absolute number, frequency, mean ± standard deviation, median, interquartile range, minimum or maximum) for.

R/R B-cell ALL patients:

- Treatment response
 - CR,
 - CRI,
 - partial remission/response,
 - progressive disease,
 - refractory disease,
 - relapsed from CR or CRI or recurrent disease,
 - other
- minimal residual disease (MRD) evaluation for patients that achieved CR or CRI and the diagnose method for MRD evaluation
- Patient status description

13. Heath care resource utilization description, considering the outpatient utilization, inpatient admissions, hospitalization length of stay, and concomitant medication prescription since diagnosis until the loss of follow-up or death from any cause. No statistical testing will be carried out. Only descriptive data will be reported (absolute number, frequency, mean ± standard deviation, median, interquartile range, minimum or maximum) for.

Newly AML patients:

- Number of hospitalizations;
- Reason for hospitalizations;
- Hospitalizations description
 - ICU period (days)
 - Procedures
 - Surgery
 - Blood transfusion
- Treatment time (descriptive and time categorized count).
- Concomitant medication description

R/R B-cell ALL patients

- Number of hospitalizations;
- Hospitalizations description
 - ICU period (days)
 - Procedures
 - Surgery
 - Blood transfusion
- Treatment time (descriptive and time categorized count).
- Concomitant medication description

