8.3.2. Outcomes

Primary outcomes

1. Description of demographic and clinical presentation characteristics at the moment of R/R B-cell ALL or AML diagnosis
2. Treatment description considering the front-line therapy and subsequent regimen(s) required for patients with R/R B-cell ALL and AML, including any systemic chemotherapy, target therapy, hematopoietic stem cell transplantation (autologous/allogenic), intrathecal chemotherapy and palliative management.

Secondary outcomes

3. Description of subtypes of AML and B-cell ALL based on the cytogenetic and molecular abnormalities, according to the WHO classification

Effective Date: 01Feb2022

4. Proportion of patients of each prognostic-risk group (favorable, intermediate, adverse) among newly diagnosed AML patients, based on cytogenetic profile
5. Description of the treatment standard from diagnosis to inclusion of R/R ALL patients
6. Description of clinically relevant events presented by AML and R/R B-cell ALL patients since treatment initiation until loss of follow-up or death from any cause;
7. The EFS will be the measure of time since diagnosis until failure to achieve complete remission (CR), or disease progression after CR, or death from any cause for both AML and R/R B-cell ALL patients;
8. The OS will be the measure of median time since diagnosis until death from any cause for both AML and R/R B-cell ALL patients;
9. The OS will also assess the proportion of AML and R/R B-cell ALL patients alive after 1, 3 and 5 years, if feasible, since treatment initiation;
10. For AML patients who achieved CR, the RFS will be the measure of time since the CR attainment until relapse or death from any cause;
11. For AML patients the response to induction and consolidation therapy will assess the proportion of patients who achieve CR, complete remission with incomplete hematological recovery (CRI), complete remission without minimal residual disease (MDR-), partial remission (PR), and progressive disease
12. For R/R B-cell ALL patients the response to the rescue treatment will access the proportion of patients with CR, complete remission without MRD-, PR, and progressive disease
13. Health care resource utilization description, considering the outpatient utilization, inpatient admissions, hospitalization length of stay, and concomitant medication prescription since diagnosis until the loss of follow-up or death from any cause.

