8.7. Data Analysis

Analyses will be descriptive in nature, as no hypothesis is being tested. Disease staging, comorbidities, demographic, clinical characteristics will be described at the date of diagnosis and/or treatment initiation for patients diagnosed with B-cell ALL R/R or AML. Treatment and clinical information will be assessed up to the most recent data available at the study enrollment. The treatments will be described in sequence according to the chronological order of administration. The duration through the number of cycles will be evaluated. Dose reduction information will also be collected. All analysis, including subgroup assessment, will be performed according to the data availability.

Continuous variables will be described as mean and standard deviation (SD), and/or as median, minimum, maximum, interquartile range (IQR, 25th and 75th percentiles). Categorical variables will be described by simple and cross contingency tabulation, with absolute frequencies and percentages. Missing values will be included in the denominators for the calculation of percentages and missing categories will be presented.

Follow-up period will be considered the time (in years) elapsed since B-cell ALL R/R or AML diagnosis until the study enrollment. It will be summarized as a continuous variable.

All time-to-event analysis will be described using Kaplan Meier methods and plots, if appropriate. The following definition and parameter analysis will be considered:

- Time to next treatment (TTNT) – considered as the time from the start date of the front-line therapy to the start date of a subsequent line of therapy. Patients without a subsequent line of therapy will be censored at study enrollment, last visit, last contact, or death, whichever comes first. It will be presented in months.
- Overall survival (OS) – considered as death from any cause from the time of initiation of diagnosis or treatment [12,13]. Patients not known to have died will be censored at study enrollment, last visit, last contact, whichever comes later. The median OS and, if feasible, the % of alive patients in 1, 3- and 5-years follow up of newly diagnosed AML and R/R B-cell ALL patients will be assessed.

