- Relapse-free survival (RFS) for newly diagnosed AML patients – considered as the date of achievement of a remission until the date of relapse or death from any cause; patients not known to have relapsed or died at last follow-up are censored on the date they were last examined, study enrollment, last contact, whichever comes later. Defined only for patients achieving CR, or CRI. The RFS will be measured as the treatment end date until next treatment initiation or date of death, whichever comes first, for all AML patients who achieved Complete remission/response (CR) or Complete remission/response with incomplete hematological/count recovery (CRI) at the end of treatment.
- Event-free survival (EFS) of newly diagnosed AML and R/R B-cell ALL patients – considered as the date of initiation of treatment (or date of diagnosis, if the previous is not available) to the date of primary refractory disease, or relapse from CR, or CRI, or death from any cause; patients not known to have any of these events are censored on the date they were last examined, study enrollment, last contact, whichever comes later. The EFS will be measured as the time since AML and R/R ALL initiation of treatment (or newly AML diagnosis and newly ALL diagnosis, if treatment date is not available) until i) treatment end date (or treatment start date of the next treatment line, if the previous is not available) when treatment response was Refractory disease(5) or Relapsed from CR or CRI or recurrent disease(6) as treatment response; ii) date of death, whichever comes first.
 - Clinically relevant events:
 - Hematological toxicities
 - Hepatotoxicity
 - Gastrointestinal toxicities
 - Tumor lysis syndrome
 - Fatigue
 - Dysgeusia
 - Alopecia
 - Muscle spasms
 - Infections

- Sepsis
- Secondary malignancy due to drug toxicity
- Death
- Other

Medical Dictionary for Regulatory Activities Terminology (MedDRA) version 2.1 (V2.1) or newer version will be used as a standardised medical terminology. Medicinal product names will be codified using World Health Organisation Drug Dictionary (WHODrug), a dictionary maintained and updated by Uppsala Monitoring Centre (UMC).

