The resource utilization (e.g., number of hospital admissions, hospitalization period, procedures during hospital admissions) will be presented, if possible, as mean number per patient per year (PPPY). According to the sample distribution, the data will be presented with a standard deviation (SD) or a 95% confidence interval (95% CI), which will be estimated with the most appropriate distribution, which may include Negative Binomial, Poisson or Gama distribution. The statistical distribution will be chosen with quantil-quantil plots (QQplots).

For each resource utilization, the PPPY will be calculated as the sum of all utilizations, divided by the follow up, for each patient. It will be summarized as a continuous variable.

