8.8. Limitations of the Statistical Analysis

Data collected from source documentation and entered into the electronic CRF will be described. No imputation for missing data will be conducted. The loss to follow-up, including patients early discontinuing the treatment, the transference of treatment institution, or patients for whom the death was not documented in their chart, consists of an intrinsic limitation of the retrospective study design.

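### For late-onset harms, the planned crude percentages count patients lost or censored at enrolment as event-free and may understate the risk

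*SAP*

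**What the plan says.** Describing clinically relevant events is a secondary objective (protocol 8.2, SAP 7.2). SAP 8.3.2 item 6 sets the window for each patient: "since treatment initiation until loss of follow-up or death from any cause". SAP 8.1 ends chart data at study enrolment or death.

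SAP 8.7.2 item 6 says that these events "will be describe by treatment line and data will be reported as absolute number, frequency" and ordinary summary statistics. It adds one timing variable, "Period of start of the event from start of first-line treatment". The classes it names are haematological, gastrointestinal and hepatic. The longer list in SAP 8.7 also contains "Secondary malignancy due to drug toxicity" and death. Protocol 9.3.2 lists graft-versus-host disease and graft failure as clinically relevant events, whereas the SAP reports post-transplant events under 8.7.2 item 2.

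SAP 8.7 gives start, event and censoring rules for overall, relapse-free and event-free survival and for time to next treatment. It gives none for clinically relevant events, apart from the general sentence "All time-to-event analysis will be described using Kaplan Meier methods and plots, if appropriate". SAP 8.8 accepts incomplete follow-up as a limitation: "The loss to follow-up, including patients early discontinuing the treatment, the transference of treatment institution" and undocumented deaths.

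**The concern.** A percentage of patients with an event estimates absolute risk over a stated period only if everyone is observed until the event, death or the end of that period. Here survivors are cut off at enrolment, some long before five years, and others transfer or disappear. The crude percentage treats all of them as never having the event.

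This hardly matters for a toxicity seen in the first weeks of a line. It matters for a harm that needs a year or more to appear, because the patients who could show it are the long survivors whose charts are most likely to be cut short. The reported frequency of secondary malignancy, and to a lesser degree of transplant complications, may then be too low. The table gives the reader no way to see by how much.

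**Working it through.** The plan states no event frequency, so there is no figure to reproduce. The calculation shows only how large the understatement could be.

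**Inputs from the documents.** Diagnosis runs from January 2015 to December 2019 and is taken as uniform. Data collection is planned for July 2021 to August 2022 (protocol section 6), and enrolment is taken as uniform from 2021.5 to 2022.67. The expected size is about 700 patients.

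**Assumed inputs.** The late harm has hazard h = 0.01 per year, starting 1 year after treatment initiation. Long-term survivors are 30% of patients; the other 70% have exponential survival with mean 0.75 years. Loss to follow-up has a constant rate L of 0, 0.10 or 0.20 per year, independent of prognosis. Treatment is taken to start at diagnosis.

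**Step 1: true 5-year cumulative incidence, with death as a competing event.**
- Long-term survivors: 1 − exp(−0.01 × 4) = 0.0392.
- Others, with death hazard m = 1/0.75 = 1.333: exp(−1.333) × 0.01/1.343 × (1 − exp(−1.343 × 4)) = 0.0020.
- All: 0.30 × 0.0392 + 0.70 × 0.0020 = 0.0131, or 9.2 of 700 patients.

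**Step 2: expected crude proportion.** This is the integral over t ≥ 1 of h·exp(−h(t − 1)) × S(t) × exp(−L·t) × G(t). Here S(t) = 0.30 + 0.70·exp(−1.333t), and G(t) is the probability that enrolment falls more than t years after diagnosis.

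| Loss per year | Crude proportion | Share of 1.31% | Events seen in 700 | Missed |
|---|---|---|---|---|
| 0 | 1.18% | 90% | 8.3 | 0.9 |
| 10% | 0.89% | 68% | 6.3 | 2.9 |
| 20% | 0.69% | 52% | 4.8 | 4.4 |

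Random-draw simulation of the same set-up gives 91%, 68% and 53%. These shares are generous to the crude figure, which also counts events after year 5. Restricted to events by year 5, they are about 80%, 63% and 49%.

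**Step 3: does the remedy recover the target?** With 2,000,000 simulated patients under the same inputs, the Aalen-Johansen estimate at 5 years is 1.31%, 1.32% and 1.32% at the three loss rates, against 1.31% true.

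**Step 4: graft-versus-host disease.** Assume onset spread evenly over the first year after transplant and ignore death. The share missed is 1 − (1 − exp(−L))/L: 0 at no loss, 4.8% at L = 0.10 and 9.4% at L = 0.20. The shortfall is about 0 to 10%.

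**Step 5: early toxicity, and why a rate is not the answer.** Assume a hazard of 0.5 per month in month 1 and zero afterwards, with lines of 2 and 6 months and no deaths. The crude percentage is 1 − exp(−0.5) = 39.3% on both lines, which is correct. Mean time at risk to first event is 0.787 + 0.607 × 1 = 1.39 months on the short line and 0.787 + 0.607 × 5 = 3.82 months on the long one. The rates are 28.2 and 10.3 per 100 patient-months, a false 2.7-fold difference.

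**The case against.** The study is descriptive, has no comparator and plans no toxicity comparison. Loss to follow-up is disclosed. With complete follow-up to death, a crude percentage is a valid absolute risk. The shortfall is a few patients in 700 and depends on assumed loss rates, and a curve resting on about nine events across two cohorts will be imprecise. All of this stands, and it limits the weight of the point. It does not remove it: follow-up is not complete here, and disclosing loss does not correct the percentage.

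A reader might go further and infer that the per-line tables make short or lethal lines look safer. The arithmetic for that exists. At a constant hazard of 0.10 per month with no deaths, a 2-month line shows 1 − exp(−0.2) = 18.1% and a 6-month line 1 − exp(−0.6) = 45.1%. But the documents give neither hazards nor line durations, and Step 5 shows no distortion when toxicity clusters early. Item 2 of SAP 8.7.2 also reports treatment duration, cycles and withdrawals with reasons for each line, and death is itself a listed event. Early death and short exposure are therefore not hidden, although they are not linked to the event counts.

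A reader might also ask why toxicity is not put on the per-patient-year scale used for resource use ("the PPPY will be calculated as the sum of all utilizations, divided by the follow up, for each patient"). Rate against proportion is a trade-off that depends on when events occur, so the absence of a rate is not in itself an error.

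**Conclusion.** The point holds for late-onset harms only. The planned percentages may understate secondary malignancy: the crude figure is about 90%, 68% and 52% of the 5-year cumulative incidence at 0, 10% and 20% loss per year, or about 1 to 4 patients in 700 (0.1 to 0.6 percentage points). For graft-versus-host disease the shortfall is about 0 to 10%. These sizes rest on the assumed event rate, survivor fraction, loss rates and onset pattern, and on enrolment at the planned dates; later enrolment would shrink the no-loss shortfall.

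The documents do not support a general claim that early toxicities are distorted or that lines are ranked wrongly. The table shells named in SAP 13.1 appear only as a file name, so they could not be checked for denominators. This is a cheap and worthwhile clarification with a small absolute gain.

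**What to change.** In SAP 8.7.2:

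- Item 6: keep the crude tables and state the denominator as the patients who started each line.
- Item 6, secondary malignancy: add cumulative incidence from treatment initiation.
- Item 2, transplanted patients: add cumulative incidence of graft-versus-host disease and of graft failure from the date of transplant.
- For these additions, use the Aalen-Johansen estimator with 95% confidence intervals, death as a competing event and censoring at last contact. Report by cohort (AML, R/R B-cell ALL), not by line.
- Name the estimator, because the general Kaplan-Meier sentence in SAP 8.7 could otherwise be applied with deaths censored, which overstates risk. With an event hazard of 0.10 per month and a death hazard of −ln(0.30)/12 = 0.1003 per month (the 70% one-year mortality that protocol 7.3 gives as an upper figure for AML at 65 or older), Kaplan-Meier gives 1 − exp(−1.2) = 69.9% at 12 months. The actual risk is 0.10/0.2003 × (1 − exp(−2.404)) = 45.4%.
- Do not present a rate per patient-month as a correction for the early toxicities.

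The cost is SAP wording and modest programming. Onset, death and last-contact dates are already needed for other planned analyses; the transplant date should be confirmed in the case report form. There will be few events and wide intervals: 9 of 700 is 1.3%, with an exact 95% interval of about 0.6% to 2.4%. Events without an onset date can appear only in the crude table, and their number must be shown. The estimator assumes that loss is unrelated to the risk of the event, and the report should say so.
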